### **10.3 SOCIOBIOLOGICAL RESPONSE TO STRESS OPTIONAL SUB-STUDY OBJECTIVES**

The investigators expect around 70-80% of patients will consent for the sub-study, which leads to the sample size around 30-40 patients for the analysis. Through this sub-study, the investigators will explore the relation between stress responses and clinical outcomes for the entire patient population and for racial subgroups. The following statistical plan will be used.

Aim 1: To evaluate the effects of stress reactivity on the development of an effective anti-tumor immune response in this patient population.

We will perform the following analyses to better understand how stress reactivity affects the anti-tumor immune response: 1) correlation analysis between the anti-tumor immune response and stress reactivity measures; 2) logistic regression in which we will regress the anti-tumor immune response of each patient on stress reactivity adjusting for covariates (e.g. age, perceived stress).

Aim 2: To evaluate the difference in terms of stress reactivity based on SES, perceptions of social stressors, and AL between racial subgroups.

Descriptive statistics of stress reactivity measures will be summarized for the entire patient population and for each racial group. Wilcoxon rank sum test or a Fisher's exact test will be used to explore the potential statistical significance among those measures (e.g. SR, clinical history, psychosocial factors (e.g., life stress events, social isolation), and genetic variants in the GR receptor gene) between racial subgroups. In addition, a discriminant analysis (e.g. quadratic discriminant analysis or nearest neighbor approach) for the entire patient population and for each racial group will be used to classify patients as high or low stress responders based on changes in cortisol during the TSST. Cross validation will be used to exam the misclassification rates.

Aim 3: To evaluate the difference between racial subgroups for the magnitude and distribution of stress responses with biological (AL) and immunologic measure of vaccine effect.

Descriptive statistics will be summarized for the AL measurements (e.g. median) at each time point (baseline, day 85, day 225, and day 730 or off study) for the entire patient population and for each racial group. We will compare the mean difference between two consecutive time points between two racial groups using a Wilcoxon rank sum test. A linear mixed model will also be fitted in which we will regress AL measurements on racial group, time, stress reactivity (may consider interaction terms) to explore the AL response profile difference. The outcome of RFS will be evaluated using Kaplan-Meier estimates and the statistical significance of difference in RFS between racial groups will be tested by a logrank test. In addition, a cox regression model will be explored.

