### **2.6.2 Clinical Model for Study of Stress Effects on Prostate Cancer and Immune Responses**

Studying stress response (SR) in conjunction with the immunotherapy clinical trial offers many advantages for identifying SR and other potential immune modulators. An optional sub-study will be made available for patients being screened to the PROSTVAC therapeutic intervention of this study. The goals of the sub-study will be to address critical empirical questions related to underlying physiological processes within the context of allostatic load (AL), by examining the mechanistic underpinnings of immune and stress responses. AL is an indicator of biological dysregulation in response to psychological and social stress and is used as a marker of psychological and social stressor impact on biological functioning (102). The trial is highly feasible and immune responses are likely to be seen in half or more of subjects, providing a wide range on immune response parameters for comparisons.

The sub-study will be the first to use a biobehavioral model to examine biological, psychological, and behavioral pathways that contribute to disease processes and outcomes in this population. Investigators will do this by characterizing stress reactivity among prostate cancer patients based on both biological factors that include individual variation in genetic variants in the GR receptor gene and chronic SES stressors. The sub-study is unique in seeking to relate stress measurements to clinical and immunologic responses. In addition to having a significant impact in terms of understanding the ways in which biological and psychological pathways may contribute to racial disparities in prostate cancer outcomes, the research is highly relevant to precision medicine.

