## 4 INVESTIGATIONAL PLAN

### 4.1 STUDY DESIGN AND DURATION

This will be a Phase II study of adjuvant PROSTVAC-V/F in subjects at high risk for relapse after radical prostatectomy. The study will be carried out at MUSC and the VAMC. The coordinating center will be at the Sponsor-Investigator Support Unit. Additional sites may be recruited as needed to ensure accrual.

We anticipate a two year period of accrual and an equal period of follow up for each subjects, or approximately four years total, from the point of completions of approvals and contracts.

The study population will be post-prostatectomy patients whose pathology reports documents one or more high risk features, including one or more of the following: pT3b or pT4, pN1, pT3a (without adjuvant radiation), positive margins, pre-operative PSA  $\geq 10$  ng/mL, Gleason score 8-10. Each site PI will be responsible for reviewing all prostatectomy cases to determine the patient's eligibility and interest in participating in the study.

Forty evaluable subjects (total 44 subjects) will be enrolled. Subjects will be treated with PROSTVAC-V/F alone. Subjects will be followed for relapse for two years after prostatectomy.

Prior to any study specific activities, the patient must be aware of the nature of his/her disease and willingly consent to the study after being informed of study procedures, the experimental therapy, possible alternatives, risks and potential benefits. IRB approval of this protocol and accompanying consent is required.

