#### 8.1.1 Measurement of Antigen-Specific T-Cell Functions

Peripheral blood samples will be collected in EDTA vacutainer tubes prior to vaccination, one week after the third immunization, and one week following final PROSTVAC administration. Red blood cells will be lysed with ACK buffer for isolation of peripheral blood leukocytes (PBL). PBLs will be frozen in 90% FBS/10% DMSO using a controlled-rate freezer, and immediately stored in liquid nitrogen. Phenotypic characterization and detection of prostate specific antigen (PSA)-specific cytokine production from T cells within previously cryopreserved PBL will be performed

simultaneously. Briefly, PBLs will be stimulated at  $5 \times 10^6$  cells per test with peptide pools consisting of sequential 15mer peptides overlapping by 11 amino acids spanning the complete human PSA protein at 1 $\mu$ g/ml/peptide (Miltenyi), 1% DMSO negative control or polyclonal activation via 50 ng/mL phorbol myristate acetate (PMA) and 1  $\mu$ g/ml ionomycin for 6 hours. Brefeldin A (10 mg/mL) will be present for the last 5 hours. Samples will be labeled to exclude dead cells by incubation with amine reactive UV Live/Dead dye (Molecular Probes). Subsequently, T cell memory subsets will be phenotyped by staining for surface antigens using monoclonal antibodies specific for CD3, CD4, CD8, CD45RA, CD45RO, CCR7 and CD64L allowing for detection of naïve, stem cell memory, central memory, effector memory and terminally differentiated effector CD4 $^+$  and CD8 $^+$  T cells. Cells are then fixed and permeabilized by treatment with BD Cytofix/Cytoperm solution (BD Pharmingen) followed by labeling with monoclonal antibodies specific for IFN- $\gamma$ , IL-17A, IL-4, and IL-10 for 30 min at 4 $^{\circ}$ C in the presence of permeabilizing staining buffer to identify predominant TH1, TH17, TH2 and Treg cytokines, respectively. Cells will be collected immediately on a BD Fortessa X-20 flow cytometer capable of detection of up to 18 parameters (Beckman Dickinson). At least 300,000 events will be collected and data analyzed using FlowJo software. Values 3-fold higher than the DMSO background are scored as positive.

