We define an “interesting” reduction in the risk of relapse to be 30% (i.e., increase in the probability of RFS from 0.6 to 0.78). Assuming a one-sided alpha = 0.1, with 30 evaluable patients, we have 80% power to detect this difference based on an exact binomial test. Thus if among 30 evaluable subjects, at least 24 are recurrence free at 24 months, we will reject the null hypothesis (2 year RFS=0.60) and conclude that the PROSTVAC intervention improves RFS relative to the current standard of care in this patient population (one-sided p-value  $\leq 0.025$ ). Anticipating a final sample size of 30 patients with 10% drop out rate, we plan to enroll 33 patients for this study.

**Interim Analysis:** An interim analysis for futility will be performed through Simon’s minimax two-stage design (Simon, 1989) when a total number of 19 patients are evaluable. The design is described as follows:

**Stopping criteria:** Stop the study if there are 11 or fewer recurrence free among the first 19 evaluable patients. Otherwise, additional patients will be accrued resulting in a total evaluable sample size of 30.

**Decision rule at N=30 evaluable patients:** Reject the null hypothesis if there are 22 or more recurrence free among the 30 evaluable patients. We claim that the PROSTVAC intervention improves RFS relative to the current standard of care in this patient population. This design controls the type I error rate at 0.1 and yields the power of 0.8.

**Safety Monitoring:** Continuous safety monitoring will be performed with early stopping rules in the case of unacceptable risk to the subjects, defined as evidence in favor of a risk of a grade 3 or greater toxicity deemed to be possibly related to treated of 25% vs. an acceptable rate of 10%. Stopping criteria are shown in the table below. The stopping rules are based on a likelihood ratio. Specifically, the likelihood ratio is calculated based on a hypothesized 10% event rate (safe) vs, a 25% event rate (unsafe) and likelihood ratios in excess of 8 (in favor of an event rate of 25%)

are considered sufficient evidence to stop the trial. For example, 7 events in 33 patients yields an event rate of 0.21, which has a likelihood ratio of 9.21 favoring a rate of 25% vs. 10%.

Stop if:	Likelihood Ratio	Observed Event Rate
3 events in $\leq 6$ patients	$\geq 9.04$	$\geq 0.50$
4 events in $\leq 12$ patients	$\geq 9.08$	$\geq 0.33$
5 events in $\leq 18$ patients	$\geq 9.13$	$\geq 0.28$

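### Aim 1 of the stress sub-study has one covariate-adjusted model, a logistic regression on a yes/no immune response that the plan does not define, although the immune readouts are graded.

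*Combined protocol and SAP*

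**What the plan says.** Section 10.3 lists two analyses for Aim 1. The first is a "correlation analysis between the anti-tumor immune response and stress reactivity measures", with no adjustment mentioned. The second is a "logistic regression in which we will regress the anti-tumor immune response of each patient on stress reactivity adjusting for covariates"; age and perceived stress are given as examples of covariates. No other adjusted model is listed for this aim.

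The readouts behind the immune response are graded. Section 8.1.1 measures PSA-specific cytokine production in T cells by flow cytometry against a DMSO control, with the rule "Values 3-fold higher than the DMSO background are scored as positive". That is an assay positivity rule, and section 10.3 does not refer to it. Section 8.1.2 reports anti-Forssman antibody as a serum titer and gives no responder threshold.

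Section 10.2.3 says that pre- and post-vaccination immune parameters will be compared and that their difference will be related to time to relapse and to stress. It names no adjusted model for the link with stress.

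Section 2.6.2 supports the sub-study on the ground that "immune responses are likely to be seen in half or more of subjects, providing a wide range on immune response parameters for comparisons".

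On size, section 10.3 expects "around 70-80% of patients will consent for the sub-study, which leads to the sample size around 30-40 patients for the analysis". No alpha, effect size or power is stated for Aim 1.

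**The concern.** A logistic model can use only whether each man responded. If the response is first measured as a fold-change or a titer, the size of the response is lost in the one analysis that adjusts for age and perceived stress. This sits badly with the rationale in section 2.6.2, which values the spread of the immune parameters. It also sits badly with section 8.1.2, which cites a report in which antibody titer tracked length of survival.

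The outcome of that model is also undefined. Two analysts could score response from the T-cell rule, from some titer threshold or from a combination, and fit different models to the same men.

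At stake is what Aim 1 can deliver from a small group: power to see a link between stress reactivity and immune response, and p-values that mean what they say when each slope rests on few responders or non-responders.

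**Working it through.** **Sample size.** The statistics section says "we plan to enroll 33 patients for this study". 0.70 x 33 = 23.1 and 0.80 x 33 = 26.4, so 23-26 men, or about 25. The stated 30-40 does not follow from 33. Section 4.1 says "Forty evaluable subjects (total 44 subjects) will be enrolled"; 70-80% of 44 is 31-35, which reaches only the lower part of 30-40. Forty men at 80% consent would need 50 enrolled.

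**Data per slope.** The model has at least three slopes: stress reactivity, age and perceived stress. Section 2.6.2 expects responses in about half or more; section 8.1.2 cites 64% for the antibody. With 25 men the smaller outcome class holds 25 x 0.50 = 12.5 or 25 x 0.36 = 9, which is about 4 or 3 per slope. With 30-40 men and half responding it holds 15-20, or 5-7 per slope.

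**Closed-form power.** The assumptions, none of them in the documents, are a two-sided 0.05 test, a normal response, k = 2 covariates independent of stress, and a true correlation r. With m = atanh(r) x sqrt(n - 3 - k), power is Phi(m - 1.96) + Phi(-m - 1.96). Cutting the response so that a share q are responders multiplies r by phi(z_q)/sqrt(q(1 - q)), which is 0.798 at q = 0.50 and 0.779 at q = 0.64.

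Example: n = 25, r = 0.4. Continuous: 0.4236 x sqrt(20) = 1.89, power 47.4%. Cut at 50%: r becomes 0.319, 0.3307 x sqrt(20) = 1.48, power 31.6%. The loss is 15.8 points.

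| r | Continuous | Cut, 50% responders (loss) | Cut, 64% responders (loss) |
|---|---|---|---|
| 0.2 | 14.8% | 11.1% (3.7) | 10.8% (4.0) |
| 0.3 | 28.3% | 19.4% (8.9) | 18.7% (9.6) |
| 0.4 | 47.4% | 31.6% (15.8) | 30.3% (17.1) |
| 0.5 | 69.0% | 47.2% (21.9) | 45.2% (23.8) |
| 0.6 | 87.3% | 64.5% (22.8) | 62.1% (25.2) |

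**Simulation of the actual models.** Same assumptions, 25 men, adjusted linear against adjusted logistic regression, r = 0.3-0.6, 50-64% responders:

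| Logistic test | True size | Power lost against linear |
|---|---|---|
| Likelihood ratio, size held at 5% | 5% | about 6-22 points |
| Likelihood ratio, uncorrected | about 7-8% | about 2-15 points |
| Wald | about 3% | about 13-37 points |

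For r = 0.4-0.6, linear power is 47-89%, against 27-72% for the size-corrected likelihood-ratio test and 20-58% for Wald. A separate set of 2,500 runs per cell put the size-corrected loss at 9-27 points. With 2,500 runs the standard error of one power estimate is up to sqrt(0.25/2500) = 1 point, and the corrected critical value is itself estimated, so single figures are good only to a few points. The closed form (9-25 points for r = 0.3-0.6) agrees with both sets in order of size.

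**Sensitivity.** At about 33 men, the middle of 31-35, the size-corrected loss is still about 11-22 points. If non-responders all sit at an assay floor and the continuous model uses ranks, its advantage at 25 men falls to about 1-18 points.

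**The case against.** Several points on the other side are sound.

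- **The size is not fixed by the documents.** A reader might infer a guaranteed minimum loss. There is none: the plan gives no effect size, alpha or choice of test. At r = 0.2 the closed-form loss is about 4 points, and at r = 0.3 the uncorrected likelihood-ratio test gives up only 2-3 points, though with an inflated size.
- **The plan does not say that it dichotomizes both readouts.** A reader might infer that the T-cell and antibody results are both cut to form the Aim 1 outcome. Section 10.3 does not say so. The aim speaks of developing an effective response, and a responder/non-responder outcome is a natural reading of that. What the documents show is an outcome left undefined.
- **The continuous data are not thrown away.** The Aim 1 correlation can use the full scale, and section 10.2.3 keeps the pre/post difference. This stands. What is missing is an adjusted model on that scale.
- **Normality flatters the linear model.** If a third to a half of the men sit at an assay floor, an ordinary linear model gains little at 50% responders. This stands, and is why ranks are offered; the gain is then smaller but does not vanish.
- **The sub-study is optional and exploratory.** Section 2.6.2 says that it is meant to show acceptability and to supply data for planning larger studies. No confirmatory claim rests on Aim 1. This limits the weight of the point, but is no reason to prefer the less efficient model.

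The proposed baseline covariate was not part of the simulations, so no power gain is claimed for it.

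**Conclusion.** The point holds as a matter of definition and efficiency. Aim 1's only adjusted model needs a binary response that the plan does not define, while graded readouts are available and have no adjusted model of their own.

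For moderate correlations and about 25 men, the cost in power is of the order of 10 to 20 points with a correctly sized test (simulated range about 6-22). It is larger with the Wald test and smaller, at the price of a 7-8% error rate, with the uncorrected likelihood-ratio test. All of this rests on the assumed r, alpha, normality, independent covariates and responder share. The loss does not depend on which enrollment figure is right, since it remains at about 33 men; the sparse-data problem does ease as numbers rise.

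The documents do not support reading this as a failed power claim, because none is made for Aim 1. Nor do they support reading it as a defect in the therapeutic trial's primary analysis, which it does not touch.

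**What to change.** In section 10.3, Aim 1:

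1. Make the main adjusted model a linear regression of the continuous post-vaccination response on stress reactivity, adjusting for the baseline value, age and perceived stress. Use log fold-change over DMSO background for PSA-specific T cells and log titer for anti-Forssman antibody. Use ranks if values are skewed or pile up at the assay floor.
2. Name the post-vaccination time point for each readout.
3. Report the responder rate descriptively. Keep the logistic model as supportive, with its cut stated for each readout and its small-sample test named.
4. Bring the expected 30-40 patients into line with the enrollment target.

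The cost is analysis text only. Baseline and post-vaccination samples are already planned (sections 8.1.1 and 8.1.2), and perceived stress is already in the survey (section 8.4). The downside is small: a scale must be chosen in advance for values at the floor, and the coefficient becomes a fold-change or rank effect instead of an odds ratio.

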### 3.3 SUB-STUDY OBJECTIVES

There are three objectives for the sociobiological response sub-study that is being conducted as part of this trial.

- To evaluate the effects of stress reactivity on the development of an effective anti-tumor immune response in this patient population
- To evaluate the difference in terms of stress reactivity based on SES, perceptions of social stressors, and AL between racial subgroups.
- To evaluate the difference between racial subgroups for the magnitude and distribution of stress responses with biological (AL) and immunologic measure of vaccine effect.

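### Aim 2 of the sub-study asks how stress reactivity relates to SES and social stressors across races, but no named analysis relates reactivity to either

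*Combined protocol and SAP*

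**What the plan says.** Section 3.3 gives the second sub-study objective as "To evaluate the difference in terms of stress reactivity based on SES, perceptions of social stressors, and AL between racial subgroups". Section 10.3 repeats it as Aim 2. Section 2.6.2 shows the intent: reactivity is to be characterised by biological factors including "genetic variants in the GR receptor gene and chronic SES stressors".

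Section 10.3 lists three analyses under Aim 2:

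- Descriptive statistics of the reactivity measures, overall and by race.
- Tests of individual measures: a Wilcoxon or Fisher test "will be used to explore the potential statistical significance among those measures". An open list of examples follows (reactivity itself, clinical history, psychosocial factors), closing with "and genetic variants in the GR receptor gene) between racial subgroups".
- A discriminant analysis, overall and within each race, to "classify patients as high or low stress responders based on changes in cortisol during the TSST", with cross-validated misclassification rates.

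The other aims in section 10.3 have different outcomes. The Aim 1 logistic regression will "regress the anti-tumor immune response of each patient on stress reactivity adjusting for covariates (e.g. age, perceived stress"). The Aim 3 mixed model will "regress AL measurements on racial group, time, stress reactivity (may consider interaction terms").

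**The concern.** An objective about reactivity in relation to SES and social stressors needs an analysis with reactivity on one side and those factors on the other. The Aim 2 tests put race on one side and a single measure on the other. They can show that reactivity differs between races, or that a stressor score does. They cannot show whether reactivity varies with the stressor.

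This matters because of the sub-study's rationale. Section 2.6.1 proposes that racial disparities in outcome may act through physiological responses to social stressors. Section 2.6.2 expects the data to identify which social, psychological and behavioural factors deserve measurement in larger studies. Both call for an estimate, with its uncertainty, of how reactivity moves with those factors. Without one, a race difference would be published with no indication of how much of it follows SES.

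**Working it through.** **1. Matching question to analysis.** For each analysis named in section 10.3, and for section 11.8:

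| Analysis | Outcome | Compared or regressed on | Reactivity against SES or stressors? |
|---|---|---|---|
| Aim 2 Wilcoxon/Fisher | each measure in turn | race | no |
| Aim 2 discriminant analysis | high/low responder | cortisol change; no other input named | not stated |
| Aim 1 correlation and logistic regression | immune response | reactivity; perceived stress only as a covariate | no |
| Aim 3 mixed model | allostatic load (AL) | race, time, reactivity | no (covers AL with reactivity) |
| Section 11.8 correlations | unspecified | unspecified | not stated |

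No row names reactivity as outcome with SES, stressors or GR genotype as predictor.

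**2. Sample size.** Section 10.3 expects 70-80% consent and 30-40 patients. With the 33 enrolled under section 10.1: 0.70 x 33 = 23.1 and 0.80 x 33 = 26.4, so 23-26. With the 44 in section 4.1: 30.8 to 35.2. The stated upper end of 40 would need 40/0.80 = 50 enrolled. The stated range is therefore not reproduced. That is a separate inconsistency, and this point does not depend on it. The figures below use 23-26 unless noted.

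**3. Illustration of size.** The documents do not give the SES gap between races (g, in SD) or the SES-reactivity correlation (r). Assumed ranges: g = 0.5-1.0 and r = 0.3-0.5. Model: reactivity = r x SES + sqrt(1 - r^2) x noise, with SES shifted by g between equal race groups and no race effect other than through SES. Tests are two-sided at 0.05.

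The within-race SD of reactivity is 1, so the true race difference is r x g: from 0.3 x 0.5 = 0.15 SD to 0.5 x 1.0 = 0.50 SD.

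Results at n = 24 (3,000 replicates per row):

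| g | r | Wilcoxon by race rejects | Race term rejects with SES in model | Power for SES slope |
|---|---|---|---|---|
| 0.5 | 0.3 | 5.5% | 5.7% | 29% |
| 0.5 | 0.5 | 7.9% | 4.9% | 71% |
| 1.0 | 0.3 | 9.5% | 4.8% | 29% |
| 1.0 | 0.5 | 19.9% | 6.0% | 71% |

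Over n = 23 to 26 the Wilcoxon range is about 5-21% and the SES power about 27-75%. At the plan's stated sizes, the Wilcoxon range is 6.5-23% at n = 30 and 8-31% at n = 40. SES power is 36-82% and 46-92% respectively.

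**4. Precision of by-race slopes.** With 12 per race and r = 0.3, the approximate 95% half-width of a standardised slope is t(10) x sqrt(1 - r^2)/sqrt(11) = 2.228 x 0.954/3.317 = 0.64. That is more than twice the assumed slope. Pooling 24 patients with a race term gives 2.080 x 0.954/sqrt(22) = 0.42.

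**The case against.** A reader might infer that the planned Wilcoxon test has an inflated false-positive rate, because it rejects in up to about 21% of trials when reactivity depends only on SES. The documents do not support that. In that scenario the races do differ in reactivity, by 0.15-0.50 SD, and the test detects a real total difference. Nothing in the plan sets an SES-adjusted race effect as the target. Under the rationale in section 2.6.1, SES may lie on the pathway from race to reactivity, so adjustment is not automatically the right comparison. At the low end of the assumptions the rejection rate is essentially nominal.

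A reader might also infer that SES is left out of the Aim 2 measures altogether. The list is only by example. It includes life stress events, and section 8.4 uses work, residence and financial subscales for these. That widens what is compared between races, but still does not relate it to reactivity.

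Three further points carry some weight:

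- The discriminant analysis may be meant to predict responder class from psychosocial and genetic inputs, since misclassification needs both a label and inputs. The text names none, so this cannot be relied on.
- Aim 3 does link allostatic load to reactivity, so the allostatic-load part of Aim 2 is partly covered.
- Section 8.1.4 promises to relate TSC22D3/GILZ variants to reactivity, and section 11.8 promises correlations among biological, social and clinical factors. The former concerns another gene and gives no method. The latter names no variables.

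Finally, section 2.6.2 says the trial is not powered for subtle racial differences in stress response. That limits the weight of the point without closing the gap.

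**Conclusion.** The gap is real and follows from the text alone: as written, Aim 2 does not answer its own question about SES and social stressors, and no other named analysis clearly does. A race difference in reactivity would stand without any account of SES.

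The 5-21% and 27-75% figures rest on assumed SES gaps and correlations, normal data, equal race groups and 23-26 participants. They illustrate scale only. Severity is minor to moderate: the sub-study is optional and exploratory, and no primary, secondary or safety conclusion of the main trial depends on it.

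**What to change.** Under Aim 2 in section 10.3, add an exploratory linear model of the TSST cortisol response on race plus one predictor at a time: SES score, perceived stress, discrimination, GR genotype. Fit it pooled over races. Choose one cortisol summary in advance, since section 8.5 leaves several open, and define the SES score from the survey items.

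Report each slope with its 95% CI. Report the race coefficient with and without SES, stating that SES may be a mediator and that the two coefficients answer different questions. Show by-race estimates descriptively only. Keep the Wilcoxon and Fisher tables as description, and state the inputs of the discriminant analysis.

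The cost is a few lines of SAP text. Survey items, genotype and cortisol are already collected under sections 8.1.5, 8.4 and 8.5, so no visits, samples or patients are added. The estimates will be imprecise and should be labelled exploratory.
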